4.2 Scientific Rationale for Study Design

This Phase 2 study is designed to provide data to support dose selection for Phase 3 based on a dose-response profile. The endoscopic healing rates for the different doses of X842 will be assessed after 4 weeks double-blind treatment. Endoscopy evaluation only at 4 weeks is based on the level and duration of acid control that can be achieved with X842. Symptom evaluation during the first 4 weeks will be assessed using the validated patient reported outcome (PRO) QOLRAD (Heartburn version) and patient diaries (RESQ-eDiary). Erosive esophagitis due to GERD is known as a chronic disease and the need for maintenance therapy is likely. To further understand the symptom pattern after 4 weeks of powerful gastric acid inhibition all patients undergoing endoscopy at 4 weeks, the end of blinded phase, will be administered 4 weeks treatment with lansoprazole 30 mg QD. Weekly and daily symptom evaluations will be done during this open-label treatment period to detect symptom pattern and symptom evaluation will be based on telephone interviews and patient diaries. Patients who will terminate the study prematurely will be scheduled for End of Study/Early Termination visit, 4 weeks after cessation of study treatment.

Evaluation of reflux related symptoms will be assessed by RESQ-eDiary, investigator's assessment and QOLRAD.

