5.3 Lifestyle Considerations

The patients must be willing to comply to the following restrictions during the entire study duration, i.e., from screening to the End of Study/Early Termination visit.

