5.3.2 Prior and Concomitant Medication and Therapy/Procedures

The patients are not allowed to concomitantly use any medication or therapy during the study likely to influence the outcome of this clinical trial. This includes:

- Agents affecting digestive organs
 - PPIs (e.g., omeprazole, pantoprazole, lansoprazole (except study medication), rabeprazole, esomeprazole, dexlansoprazole, dexrabeprazole, vonoprazan, etc.),
 - H₂ receptor antagonists (e.g., cimetidine, ranitidine, famotidine, nizatidine, niperotidine, roxatidine, lafutidine, ebrotidine, etc.),
 - muscarinic receptor 3 antagonists (e.g., atropine, scopolamine, hyoscyamin, ipratropium, tiotropium, pirenzepine, darifenacin, oxybutinin, refefenacin, etc.),
 - gastrointestinal prokinetic agents (e.g., metoclopramide, cisapride, domperidone, bromopride, alizapride, clebopride, itopride, cinitapride, mosapride, etc.),
 - anti-cholinergic agents (e.g., pirenzepine, telenzepine),
 - prostaglandins (e.g., misoprostol, enprostil, etc.),
 - antacids,
 - anti-gastrin agents (e.g., proglumide, oxethazaine, etc.).
- Medications that may affect the metabolism of X842 or linaprazan (cytochrome P450 [CYP] inhibitors and inducers) and medications that may be affected by X842 or linaprazan (substrates of CYP enzymes and drug transporters). For a comprehensive list, see Section 10.9 (Appendix 9),
- Medications contraindicated for use in combination with lansoprazole,
- Medications with reported drug–drug interactions with lansoprazole (warfarin, clopidogrel, ketoconazole, itraconazole, digoxin, tacrolimus, theophylline, methotrexate) and
- *H. pylori* eradication therapy (antibiotics along with PPI).

Patients are not permitted to undergo surgical intervention (e.g., fundoplication) for reflux disease or other antireflux procedures during study participation. Any planned major surgery within the duration of the study is exclusionary.

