6.6.1 Rescue Medication

All restrictions regarding the use of medications or therapies which are likely to influence study outcome are applicable for the entire duration of the study (please refer to Section 5.3.2 for not permitted medications).

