6.8 Intervention After the End of the Study

There will be no treatment with X842 or lansoprazole available, provided by Sponsor, after End of Study participation. Following discontinuation of study treatment some patients may need additional therapy for their erosive esophagitis due to GERD. The Investigator should ensure patients re-establish care with a physician during the open-label treatment period in order to avoid a lapse.

7 Discontinuation of Study Drug and Patient Discontinuation

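### Read literally, the protocol leaves patients who stop study drug before the 4-week endoscopy about 28 days with neither study drug nor a permitted acid suppressant

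*Protocol*

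**What the plan says.** - **Visit timing.** Protocol Section 4.2, repeated in the SAP introduction (Section 1): "Patients who will terminate the study prematurely will be scheduled for End of Study/Early Termination visit, 4 weeks after cessation of study treatment". Section 7.2, the discontinuation procedure, asks for the same assessments where possible and gives no timing of its own.
- **Length of the restrictions.** Section 5.3 applies them "during the entire study duration, i.e., from screening to the End of Study/Early Termination visit".
- **What is restricted.** Section 5.3.2, which sits under 5.3: "The patients are not allowed to concomitantly use any medication or therapy during the study likely to influence the outcome of this clinical trial". Its list names PPIs, H2 antagonists and antacids. The only exemption from the PPI entry is lansoprazole supplied as study medication.
- **Rescue.** Section 6.6.1 names no rescue drug. It says that restrictions on therapies "which are likely to influence study outcome are applicable for the entire duration of the study", and it makes no exception for patients who have stopped.
- **Open-label supply.** Section 4.2 gives open-label lansoprazole to patients who have the 4-week endoscopy. The schedule of assessments dispenses it only at Visit 5.
- **Need for treatment.** Section 4.2 calls erosive esophagitis a chronic disease in which maintenance therapy is likely to be needed. Section 6.8 adds: "Following discontinuation of study treatment some patients may need additional therapy for their erosive esophagitis due to GERD". It continues: "The Investigator should ensure patients re-establish care with a physician during the open-label treatment period in order to avoid a lapse".

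**The concern.** Each statement is reasonable alone. The difficulty comes from combining them. The restrictions end at a visit, and for early terminators that visit is placed 4 weeks after the last dose. A patient with erosive disease who stops blinded drug early and remains under observation therefore seems to have no study treatment and no permitted acid suppressant for those 4 weeks, although the same protocol expects some such patients to need treatment.

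The main stake is patient care: a site that follows the text literally would withhold therapy that Section 6.8 anticipates. The second is consistency. A site that treats before the Early Termination visit uses a listed drug, and SAP Section 4.4.2 has a deviation category for disallowed medications. Sites may resolve the ambiguity differently, so safety and symptom data from this interval could come from treated patients at some sites and untreated patients at others.

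**Working it through.** The plan gives no figure for this interval, so there is none to reproduce. The check sets the passages side by side and uses calendar arithmetic on the visit schedule.

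**Inputs**
- Early Termination visit: 4 weeks after cessation (Protocol 4.2; SAP 1).
- Restrictions end: at the End of Study/Early Termination visit (Protocol 5.3).
- Visit 5: Day 28, window -2/+5 (Protocol Table 1).
- Visit 9: Day 56, window ±3 (Protocol Table 1).
- Open-label lansoprazole: 4 weeks, from Visit 5 (Protocol 4.1, Table 1).

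**Step 1: patient who stops in the blinded phase without the 4-week endoscopy**
- Time under restriction without study drug = visit day − day of last dose = 4 × 7 = 28 days.
- Example: last dose on Day 10 gives a visit on Day 10 + 28 = Day 38. No open-label supply is dispensed in between.

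**Step 2: completer, for comparison**
- Visit 5 falls between Day 28 − 2 = 26 and Day 28 + 5 = 33.
- Open-label supply ends between about Day 26 + 28 = 54 and Day 33 + 28 = 61.
- Visit 9 falls between Day 56 − 3 = 53 and Day 56 + 3 = 59.
- Nominal gap = 56 − (28 + 28) = 0 days. Largest gap = 59 − 54 = 5 days.

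The long interval is therefore specific to early terminators.

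**Step 3: does any other section release the patient?**
- 5.3.2 and 6.6.1: no exception after stopping.
- 7.2: neither times the visit nor lifts the restrictions.
- 7.1: discontinuing does not affect the right to future care, but the medication list is not mentioned.
- 8.4.7: adverse events are treated according to clinical practice at the investigator's discretion. The listed drugs are not expressly exempted, and the section concerns adverse events, not the underlying disease.
- 6.8: recognises the need for therapy, but its instruction belongs to the open-label period.

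**Step 4: who falls outside the problem**
- Consent withdrawn: Section 7.1 ends further study observation.
- Lost to follow-up (Section 7.4): there may be no Early Termination visit.

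**Step 5: which analyses are touched**
- Primary endpoint: SAP 4.10.1.3 counts missing healing as non-response. A patient without the 4-week endoscopy is a non-responder whatever is taken afterwards. A patient who stops in the open-label period has normally had the endoscopy already.
- Adverse events: the treatment-emergent window in SAP 4.11.1 is 30 days after the last dose. Since 28 < 30, the whole interval is inside it.
- QOLRAD: collected at Visits 2, 3, 4, 5 and 9, so a patient who has left the schedule adds at most one later record.
- Per Protocol Set: Protocol 4.4 counts attendance at the Early Termination visit as completion, and the set excludes certain major deviations. Membership could depend on how therapy taken after stopping is classified. That is settled in a separate specification and at the blinded review, so the documents do not show the answer.

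**The case against.** The strongest reply is that there is no outright contradiction. A reader might infer that the restrictions breach an instruction to avoid a lapse in therapy. Section 6.8 does not say that. Its heading and opening concern the time after study participation, the lapse is left unqualified, and the sentence is about returning to a physician's care during the open-label period. A patient who stops on Day 10 never enters that period, so the sentence does not reach this patient. This objection stands: for blinded-phase stoppers the defect is a gap and a conflict by implication. For a patient who stops during the open-label period, Section 6.8 does apply and the conflict is more direct.

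The second reply is that Sections 7.1 and 8.4.7 already protect the patient: future care is unaffected, and worsening symptoms might be treated as an adverse event. These passages soften the restrictions. They do not lift them, and 8.4.7 becomes one more section to reconcile.

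The third reply concerns scale. A reader might infer that every patient who stops before Visit 5 is affected, or that the allowance of 240 − 200 = 40 non-evaluable patients (40/5 = 8 per arm) gives the number. Neither follows. Withdrawn consent and loss to follow-up remove some patients, and Section 7.2 asks for the visit only where possible. The sample-size sections are blacked out, so it cannot be seen what evaluable means or how many of the 40 would be early stops. Unusable images or ineligibility could also account for some.

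Finally, use of a listed drug is not automatically a major deviation. SAP 4.4.2 lists categories and leaves classification to the deviation specification and the blinded review.

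**Conclusion.** The point holds as a gap between sections. For a patient who stops before the 4-week endoscopy and stays under observation, the text read literally gives about 28 days with neither study drug nor a permitted acid suppressant, against nominally 0 and at most about 5 days for a completer. This assumes that the timing in Section 4.2 is applied as written and that Section 5.3 governs the list in 5.3.2, as its placement implies.

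The number of patients affected cannot be derived from the documents. A reader might also infer that the healing result is at risk. The documents do not support that, because non-response imputation leaves little room for an effect on the primary endpoint. What remains is a question of patient care and site consistency, with a secondary effect on adverse-event and late symptom data and possibly on Per Protocol Set membership.

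**What to change.** Reconcile Protocol Sections 4.2 (and the SAP introduction), 5.3, 5.3.2, 6.6.1, 6.8, 7.2 and 8.4.7. They should state one consistent end point of the medication restrictions for a patient who has stopped study drug but has not reached the Early Termination visit. Section 6.8 should also cover patients who never enter the open-label period. The Protocol Deviation Specification should then follow the same rule. The sponsor decides what that clinical rule is.

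No new data item is needed: Protocol Section 8.1.6 already requires start and stop dates for concomitant medication up to the End of Study/Early Termination visit. The cost is protocol wording and a letter to sites, with no extra visits or procedures.

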The dose levels in this study (CX842A2201) are selected to accommodate for severe eGERD patients representing a "harder to treat" population. The Phase 1 PK/PD (intragastric pH over 48 hours) study (CX842A2103) on repeated BID dosing of 50 mg, 100 mg and 150 mg X842 during day 1 and 2 and once daily on day 3 showed a clear dose response. The 50 mg dose provided acid control (intragastric pH > 4) during 68% of time while the corresponding figure for the 150 mg dose was above 90% of time. In this study (CX842A2201), the lowest dose, 25 mg X842 BID is selected to provide a lower or similar pH control as seen during lansoprazole 30 mg QD at steady-state. The 25 mg dose of X842 should therefore provide healing rates that are lower or similar to what is seen after lansoprazole 30 mg QD. The highest dose 100 mg X842 BID is selected to provide intragastric pH control during 85% of the time. The intermediate X842 doses of 50 mg BID and 75 mg BID are selected to provide acid control of approximately 70-80% of the time. The predicted efficacy of the 75 mg and 100 mg doses of X842 are assumed to be superior to lansoprazole 30 mg QD, i.e., the recommended daily healing dose for patients with esophagitis.

4.4 End of Study Definition

All patients who participate in this study and complete Visit 9 (End of Study/Early Termination) visit are considered to have completed the study (Table 1).

The end of the study is defined as the date of the last visit of the last patient in the study.

5 Study Population

Prospective approval of protocol deviations to eligibility criteria, also known as protocol waivers or exemptions, are not permitted.

The patients possibly eligible will be identified as the follows:

1. Patients identified during their routine endoscopy:
 - Patients must have erosive esophagitis identified during the routine endoscopy, before being considered for study screening (prior to signing the ICF).
 - This routine endoscopy will also serve as the index endoscopy in the study and the report should contain the endoscopy findings using the Los Angeles (LA) classification.
 - This routine endoscopy must be obtained within 7 working days of planned randomization, please refer to [Inclusion criterion #4](#).
2. Patients invited for screening upper endoscopy based on their past medical history (both criteria must be met):
 - a) LA grade C or D disease within the past 5 years before screening, demonstrated with endoscopy (endoscopy report issued by a gastroenterologist/endoscopist is accepted)
 - b) In the Investigator's judgement the patient presents clear symptom relapse: patient may be treated with PPI, discontinued PPI treatment (patient's decision) or is being treatment naïve.

For patients invited for screening upper endoscopy, the ICF will be signed prior to the endoscopy. The screening procedures must start with endoscopy and in case the patient doesn't show LA grade C or D erosions, the rest of the screening procedures must not be conducted. This screening endoscopy must be obtained within 7 working days of planned randomization.

The index/screening endoscopy video/digital image will be anonymized and saved for central storage. Imaging data must meet quality standards for adequate LA grading and must be accompanied by a report and videos/digital images to allow retrospective analysis of the endoscopy findings.

Investigators must keep a record of all screened patients even if they were not subsequently randomized in the study. This information is necessary to verify that patients were selected

without bias. The reason for screening failure should be stated for all patients screened but not randomized. The reason for withdrawal should be stated for all patients included but not completed study.

A screening number will be allocated to each patient in connection to the informed consent process at the screening visit. The screening number will allow identification of patients irrespective of their possible eligibility for the study.

For eligible patients, a randomization/treatment number will be assigned.

5.1 Inclusion Criteria

For inclusion in the study, patients must fulfill the following criteria:

1. Written informed consent must be obtained before any study related assessment is performed.
2. Male or female patient aged 18-75 years inclusive at the time of obtaining the informed consent.
3. Body mass index (BMI) ≥ 18 and ≤ 40 kg/m² at screening
4. Gastroesophageal reflux disease with endoscopically confirmed erosive esophagitis:
 - LA grade C or D ≤ 7 working days before randomization (with or without historical PPI treatment)
or
 - LA grade A or B ≤ 7 working days before randomization
and
 - history of treatment with standard healing course of PPI* for minimum of 8 weeks prior to screening and ≤ 7 working days of non-treatment during this period**.
and
 - at least partial symptom response during the minimum of 8 weeks of PPI treatment.

Note: Partial symptom response is defined as a clear symptom improvement (heartburn or regurgitation) after start of the PPI treatment course. To qualify, the patient's response must be YES to the Investigator's standardized question to the patient: Did you feel a clear symptom improvement in heartburn or regurgitation after you started the PPI treatment course?

* All PPIs EXCEPT lansoprazole

** Non-treatment days are counted from the last day of standard healing course of PPI therapy until endoscopy used for eligibility assessment demonstrating erosive esophagitis due to GERD.”

5. Willing and able to comply with all aspects of the protocol (including PK sampling, capsule swallowing, diary completion, etc.)

5.2 Exclusion Criteria

Patients are excluded from the study if any of the following criteria apply:

1. Female patients of childbearing potential, defined as all women physiologically capable of becoming pregnant, unless they are using one of the following adequate methods of contraception during dosing and for at least seven (7) days after the last dose of study medication:
 - Total abstinence (when this is in line with the preferred and usual lifestyle of the patient). Periodic abstinence (e.g., calendar, ovulation, symptothermal, post-ovulation methods) and withdrawal are not acceptable methods of contraception
 - Female sterilization (have had surgical bilateral oophorectomy with or without hysterectomy) or tubal ligation at least 6 weeks before taking the first dose of study treatment. In case of oophorectomy alone, only when the reproductive status of the patient has been confirmed by follow-up hormone level assessment.
 - Male sterilization (at least 6 months prior to screening). For female patients on the study, the vasectomized male partner should be the sole partner for that patient.
 - Placement of a non-hormonal IUD
 - Double barrier methods of contraception: condom in combination with occlusive cap (diaphragm or cervical/vault cap) with spermicidal foam/gel/film/cream/vaginal suppository

Note: Patients who are already on hormonal contraceptives prior to study enrollment must agree to:

- replace hormonal contraception with double barrier method or
- use double barrier contraception method in addition to the hormonal contraceptives

2. Female patients of non-childbearing potential not requiring a contraceptive method, are defined as
 - Pre-menopausal females with a documented tubal ligation or hysterectomy; or
 - Post-menopausal females defined as at least 12 months of amenorrhea (without an alternative medical cause) and confirmed with simultaneous serum follicle stimulation hormone (FSH), consistent with post-menopausal status according to central laboratory ranges.

Patients who do not meet one of these two criteria above will be considered being of childbearing potential and are excluded unless using one of the adequate contraceptive methods defined in [Exclusion Criterion #1](#).

3. Male patients with a partner of childbearing potential, unless they are willing to use condoms in combination with a second method of adequate contraception (e.g., double barrier method), and they agree not to father a child during dosing and for at least seven (7) days after the last dose of study medication. Each male patient will be considered as potent unless surgically sterilized (at least 6 months prior to screening).
4. History or presence of any clinically significant cardiovascular, respiratory, hepatic, renal, gastrointestinal, endocrine, hematological, or neurological disease or disorder which, in the opinion of the Investigator, may either put the patient at risk because of participation in the study, or influence the study results or the patient's ability to participate in the study
5. Patients with so-called "alarm features" in symptomatology, like odynophagia, severe dysphagia, bleeding, weight loss, anemia, and blood in stool pointing to a possible malignant disease of the gastrointestinal (GI) tract. Exclusion can be based on symptoms only.
6. Present clinically significant psychiatric diagnosis, at discretion of the Investigator
7. History of malignancy of any organ system (other than completely treated localized basal cell carcinoma or non-metastatic squamous cell carcinoma of the skin or in situ cervical carcinoma), within the past 5 years.
8. Presence of esophageal ulcer, stricture, Barrett's esophagus or suspected esophagitis secondary to infection, inflammatory disease, ingestion of erosive chemicals or history of any surgical or medical condition which might significantly alter the GERD status or the absorption, distribution, metabolism or excretion of drugs. The Investigator is to be guided by evidence of any of the following: history of major gastrointestinal surgery such as gastrectomy, gastroenterostomy, bowel resection or transjugular intrahepatic portosystemic shunt (TIPS)
9. Known severe atrophic gastritis
10. Any planned major surgery within the duration of the study
11. Any clinically significant laboratory parameter outside reference value that, in the opinion of the Investigator, may suggest a new or insufficiently understood disease, may present an unreasonable risk to the patient as a result of his/her participation in the study, or may interfere with study assessments.

Any of these screening laboratory tests results are exclusionary:

- Serum ALT or AST $> 1.5 \times$ the upper limit of normal (ULN) for the central laboratory conducting the test
- Serum Total Bilirubin $> 1.5 \times$ ULN for the central laboratory conducting the test
- Serum Creatinine $> 1.5 \times$ ULN for the central laboratory conducting the test
- Estimated glomerular filtration rate ≤ 59 mL/min (calculated using the Modification of Diet in Renal Disease equation)

12. History of a positive result for human immunodeficiency virus (HIV), Hepatitis B surface antigen (HBsAg), antibody to Hepatitis B core antigen (anti-HBcAg), or antibody to Hepatitis C virus (anti-HCV) or presence of these findings on screening

Note: Patients with positive anti-HBcAg along with negative HBsAg at screening will not be excluded IF they have a positive local anti-HBs test results not older than 6 months and active HBV infection has been ruled out by the Investigator.

13. After 10 min supine rest at the time of screening, any vital signs values outside the following ranges:
 - Systolic blood pressure (BP) > 160 mmHg or < 90 mmHg
 - Diastolic BP > 100 mmHg or < 60 mmHg
 - Heart rate < 40 or > 95 beats per min
14. History of long QTc syndrome (e.g., QTc \geq 450 ms for males and \geq 470 ms for females)
15. Cardiac arrhythmias or any clinically significant abnormalities in the resting 12-lead ECG at the time of screening, as judged by the Investigator
16. History of severe allergy/hypersensitivity or ongoing allergy/hypersensitivity, as judged by the Investigator, or history of hypersensitivity to drugs with a similar chemical structure or class to X842 or lansoprazole
17. Administration of another new chemical entity (defined as a compound which has not been approved for marketing) or has participated in any other clinical study that included drug treatment with less than one month between administration of last dose and first dose of IMP in this study.
18. Positive screen for drugs of abuse at screening (for the list of drugs for testing please refer to the laboratory manual).
19. Current or history of alcohol, drug abuse and/or use of anabolic steroids within 2 years prior to screening
20. Women who are pregnant or breast feeding.
21. Patient is an employee of the Investigator or study site, with direct involvement in the proposed study or other studies under the direction of that Investigator or study site, as well as family members of the employees or the Investigator.
22. Patients who have previously participated (completed or withdrawn) in this study
CX842A2201

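### Exclusion 2 has no minimum interval for tubal ligation, so the 6-week condition in exclusion 1 has no effect for a documented ligation

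*Protocol*

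**What the plan says.** All of this is current text in Protocol Section 5.2.

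- **Exclusion 1** applies to women of childbearing potential, "defined as all women physiologically capable of becoming pregnant", unless they use a listed method. Ligation is on the list with a waiting time: "tubal ligation at least 6 weeks before taking the first dose of study treatment".
- **Exclusion 2** sets the opposite class: "Female patients of non-childbearing potential not requiring a contraceptive method, are defined as". Its first bullet reads "Pre-menopausal females with a documented tubal ligation or hysterectomy; or". Documentation is required, but no time since surgery is given.
- **The link** between the two is exclusion 2's closing sentence: "Patients who do not meet one of these two criteria above will be considered being of childbearing potential". Those women are excluded unless they use an exclusion 1 method.

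Pregnancy testing and contraception follow the classification. Schedule of Assessments footnote 7, Section 8.1.8 and footnote 1 to the laboratory table in Section 8.3.5 confine pregnancy tests to women of childbearing potential. Section 5.3.1 places the duty to use contraception on the same group of women.

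**The concern.** The protocol attaches a waiting period to ligation in one criterion and drops it in the next. The woman affected is pre-menopausal with a recent, documented ligation. Exclusion 1 does not yet count her surgery as protection. Exclusion 2 counts it at once and removes the need for any other method.

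At stake is dosing a woman with an investigational drug, without contraception and without a scheduled pregnancy test, during a period in which the protocol's own condition says her ligation is not yet enough. The surgical history interview (Section 8.1.5) should bring the ligation to light, but it does not restore the waiting time. Section 5 allows no eligibility waivers, so sites have to work from the text as it stands.

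**Working it through.** The plan gives no figure to reproduce. The check sets the criteria side by side and runs one test case through them.

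**Inputs**
- Exclusion 1: ligation counts from 6 weeks before first dose. 6 × 7 = 42 days, so a ligation 0 to 41 days old falls short.
- Exclusion 2: a documented ligation counts with no interval.
- Scheduled pregnancy tests for women of childbearing potential (Table 1, footnote 7): serum at screening, urine at Visit 5, urine at End of Study/Early Termination. 1 + 1 + 1 = 3.

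**Test case: a pre-menopausal woman with a documented ligation**

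| Ligation to first dose | Classified under exclusion 2 first | Read from exclusion 1 first |
|---|---|---|
| 42 days or more | No other method; 0 of 3 tests | Ligation accepted, no other method; 3 of 3 tests |
| 0 to 41 days | No other method; 0 of 3 tests | Ligation not accepted, another listed method needed; 3 of 3 tests |

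**What the table shows**
1. In the exclusion 2 column the two rows are identical. The 6-week condition changes nothing for a documented ligation. This is the defect.
2. For contraception, the two columns differ only in the 0 to 41 day row.
3. For testing, the columns differ in both rows, because ligation is listed in both criteria. The testing contrast is therefore not a feature of the 42-day window. What is specific to the window is that the woman goes untested and without another method while exclusion 1 would not yet rely on her surgery.

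**Is the missing interval deliberate?** Tubal ligation or male sterilisation counts at four places in exclusions 1 to 3:
- ligation in exclusion 1: 6 weeks before first dose
- male partner in exclusion 1: 6 months before screening
- ligation in exclusion 2: none
- male patient in exclusion 3: 6 months before screening

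Three of the four carry an interval. Exclusion 3 places its interval inside a definition of status: "Each male patient will be considered as potent unless surgically sterilized (at least 6 months prior to screening". The protocol already uses the form that exclusion 2 lacks. This suggests an oversight but does not prove one.

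**The case against.** The strongest reply is that the text does settle the order. Exclusion 1 is limited to women of childbearing potential, exclusion 2 says who is outside that class, and its closing sentence sends only the remaining women back. A documented ligation is therefore dealt with in exclusion 2, and exclusion 1 never opens. The lead-in, "Patients are excluded from the study if any of the following criteria apply", does not change this, since exclusion 1 does not apply to her. This stands as the better reading. A reader might infer that the protocol gives no indication of which criterion governs, but the closing sentence does not support that. Accepting this order does not cure the problem, because it is what removes the 6-week condition for documented ligations.

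It can be added that the condition keeps some work: it still governs an undocumented ligation, and on one parsing it may also cover oophorectomy. That is fair. It limits the loss of effect to documented ligations, but those are the ones a site is most likely to accept.

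The count of three in four is also open to criticism. It mixes male and female procedures, uses different reference dates, and leaves out hysterectomy and oophorectomy. It is supporting evidence only, and the point holds without it.

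Finally, exclusion 20 bars pregnant women, and Section 8.4.8 stops treatment on pregnancy or suspicion of it, whatever the classification. Both protections are real. Neither schedules a test for her.

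**Conclusion.** The point holds at minor severity. On the most natural reading of Section 5.2, the 6-week condition on tubal ligation has no effect for a pre-menopausal woman whose ligation is documented. One ligated 0 to 41 days before first dose can be dosed with no contraception and no scheduled pregnancy test.

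The size is small. The documents give neither the share of women nor the frequency of recent ligation, so no patient count can be derived; it is likely very low. Only patient safety is involved.

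Two assumptions carry the conclusion: that sites classify under exclusion 2 first, as its closing sentence suggests, and that the 6 weeks was meant to apply to documented ligations. The protocol gives no reason for the 6 weeks. The finding therefore holds the protocol to its own condition and makes no estimate of pregnancy risk.

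A reader might also infer from the test counts that the gap of three tests against none arises only in the 42-day window. It does not: on an exclusion 1 first reading it exists for older ligations too. Nothing here suggests that a ligation older than 6 weeks is handled wrongly for contraception.

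**What to change.** In the first bullet of exclusion 2, replace the bare ligation item with a documented ligation done 6 weeks or more before the first dose of study treatment. Follow it with a comma before the hysterectomy item, so that the interval does not attach to hysterectomy.

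A more recent ligation then fails the exclusion 2 definition. The closing sentence sends the woman to exclusion 1, where she needs another listed method and is pregnancy-tested as a woman of childbearing potential. Footnote 7, Section 8.1.8 and the laboratory footnote need no edit because they follow childbearing status. The change does not remove the double listing of older ligations and is not meant to.

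The cost is one phrase of protocol wording, with no effect on sample size, visits or analysis. The SAP amendment (Section 3) was written after unblinding, so the practical use is in any later protocol that reuses these criteria.
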